3.0 Study Endpoints/Events/Outcomes

3.1 Primary Endpoint/Event/Outcome:

SOCIAL PROTOCOL (HRP-580)

PROTOCOL TITLE:

VERSION DATE:

The primary study outcome is referral rates. Note that parent engagement will also be measured in a separate arm of the study, captured in a separate IRB protocol.

We will also assess acceptability, feasibility, and appropriateness of the training and referral process to PC personnel. Note that the acceptability of the referral process among parents will also be measured in a separate arm of the study, captured in a separate IRB.

3.2 Secondary Endpoint(s)/Event(s)/Outcome(s):

The secondary outcome is PC personnel communication skills.

4.0 Study Intervention(s)/Interaction(s)

4.1 Description:

Participating providers will be randomly assigned to either a communication skills training and training in the referral process or to receive a written description of the referral process.

Data will be collected in the form of online surveys, audio recorded responses to vignettes, focus groups, and referral counts.

We will develop 5 brief vignettes to measure communication skills related to parent engagement (e.g., “After learning about a parent spanking their child, you decide to raise the topic of discipline; how do you start?”). Verbal responses will be audio-recorded directly in the online survey. Because the communication skills in the PC training will mirror the therapist skills in GenPMTO, we will adapt relevant components of the Fidelity of Implementation Rating System⁴¹ and two coders will rate the quality of response, accounting for confronting, teaching, supporting, and facilitating.

All PC personnel in the study (including control and training conditions) will receive a written summary and process map of the referral process. The referral process will be modeled on an Institute for Healthcare Improvement (IHI) report, which documents a 9-step process for “closing the loop” on referrals. The referral process, in short, is that the medical care provider will make a referral using a designated form, the therapist will confirm receipt and take over responsibility for communication with the family, and the therapist will communicate with PC personnel at specified intervals with specified follow-up steps. PC personnel in both arms of the study will be informed of the referral process because a specified referral process constitutes a minimal implementation step, which should reasonably accompany a new resource; this will allow us to examine the effectiveness of communication skills training (which is also recommended in the IHI report) over and above the referral process.

The training will focus on communication skills based on key constructs in the Health Belief Model and motivation/resistance research. Research of the Health Belief Model⁴² has shown that perceived benefits and perceived barriers are predictive of participation in preventive services;⁴³ which hold for preventive parenting programs.^{44, 45} For example, parents may not see benefits of prevention programs when children are young. Perceived (and real) barriers to attending parenting programs also adversely impact attendance and must be addressed to engage parents.¹⁶ In addition, studies of parent non-compliance within interventions has shown that when parents feel confronted and taught, the likelihood of resistance to change increases.⁴⁶ This research informs the communication skills therapists learn to use in GenPMTO and will be included in the PC personnel training.⁴⁷ These skills involve conveying information in motivating and supportive ways to facilitate and empower parents to change. The training will focus on: (1) conveying the benefits of parenting programs, (2) knowledge

SOCIAL PROTOCOL (HRP-580)

PROTOCOL TITLE:

VERSION DATE:

of and responses to common perceived barriers to attending parenting programs, and (3) skills and strategies to effectively motivate and refer parents in ways that are least likely to elicit resistance. The training will include a 30-minute online introduction and a 56-60 minute in-person meeting. It will include a theoretical background and experiential learning; each step of the referral process will be demonstrated and role-played.

5.0 Procedures Involved

5.1 Study Design:

We will use a sequential mixed-methods approach to address the research question: Are the referral process and training acceptable, feasible, and appropriate? We will randomize PC personnel within two FQHC clinics to receive training or to a control group in which they only receive the information on how to refer to therapists who provide eHealth GenPMTO. We will survey the PC personnel in the training and control arms after the training and after the pilot year. We will conduct focus groups with a subset of PC personnel to gain a deeper understanding of survey results. The mixed methods design will be sequential in structure, with the purpose of the qualitative research being to explain and expand on survey results (i.e., QUAN->QUAL).⁴⁸⁻⁵⁰ We will use a small-scale randomized trial to address two pilot effectiveness research questions: Does the PC personnel training have a direct effect on parent engagement? Is there an indirect effect through the mechanism of improved communication skills? We hypothesize that point estimates will indicate such effects.

5.2 Study Procedures:

[figure not shown]
A diagram of the study flow for providers is provided below.

PC personnel will be randomized to the training group or a control group. Personnel in the training group will participate in surveys after the completion of PC personnel training; PC personnel in both training and control group will complete surveys after the year-long pilot study. We will recruit personnel from the training group for a focus group (or interviews if scheduling is a barrier), and personnel from the control group for a focus group (or interviews) after the post-pilot surveys are completed. In addition, we will request aggregate referral rate data from HCMC medical records. For each provider, we will request the number of children ages 2-5 seen during the pilot year and the number of referrals made.

SOCIAL PROTOCOL (HRP-580)

PROTOCOL TITLE:

VERSION DATE:

Provider data will be collected in the form of online surveys, focus groups (which will be recorded and transcribed), and referral source counts. Providers will complete a survey immediately following their training or review of written referral process and after the pilot year; each survey will take 30 minutes. The survey will include 5 brief vignettes to measure communication skills related to parent engagement (e.g., “After learning about a parent spanking their child, you decide to raise the topic of discipline; how do you start?”). Verbal responses will be audio-recorded directly in the online survey. Because the communication skills in the PC training will mirror the therapist skills in GenPMTO, we will adapt relevant components of the Fidelity of Implementation Rating System⁴¹ and two coders will rate the quality of response, accounting for confronting, teaching, supporting, and facilitating.

Construct	Measure	Time administered
Demographics	Age, gender, race/ethnicity, discipline, years of experience, etc.	Post training, post pilot year
Acceptability	Acceptability of Intervention Measure (4 items)	Post training, post pilot year
Acceptability	Readiness to Change Assessment, patient preferences (4 items)	Post training, post pilot year
Appropriateness	Intervention Appropriateness Measure (4 items)	Post training, post pilot year

SOCIAL PROTOCOL (HRP-580)**PROTOCOL TITLE:****VERSION DATE:**

		year
Feasibility	Feasibility of Intervention Measure (4 items)	Post training, post pilot year
Communication Skills	Vignettes (5 items), coded with adapted GenPMTO fidelity manual	Post training, post pilot year
Declined referrals	Whether clinician made any referrals, parent responses, whether and how frequently parents declined a referral, and reasons for declining (5 items)	Post pilot year

Participants will also be invited to participate in a focus group, which will take 90 minutes. The focus group will address the acceptability, appropriateness, and feasibility of the training and referral process.

The following participant-facing data collection forms are attached:

- Provider survey (after the training, after the pilot year)
- Provider focus group script
- Provider referral count form

5.3 Follow-Up:

NA

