11.0 Number of Participants**11.1 Number of Participants to be Consented:**

We plan to enroll 35 medical providers who work with children between three-five years old at the two clinics. Half of the participants will be randomly assigned to each study arm; n=15 of the 35 will be recruited for focus groups.

SOCIAL PROTOCOL (HRP-580)

PROTOCOL TITLE:

VERSION DATE:

This pilot study is not meant to provide conclusive fully-powered effectiveness results. These analyses will be useful in guiding focus group topics, and generating effect size estimates and variance components to guide proceeding with an R01 application for a fully-powered randomized trial.

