As benchmarks for comparison, other studies that have targeted referral practices and behaviors have found medium-sized effects (e.g., $d=.50-.66$) on some PC practice outcomes. In these same studies, researchers reported attrition ranging from 0-15%.³⁴⁻³⁵ These estimates correspond with minimum sample sizes ranging from 76-148 to achieve power of .80 to detect a difference between the study arms. Our sample size of 35 results in power of .47 to detect an effect of .66, or power of .61 with a one-tailed test. These power analyses illustrate why this study is needed in preparation for an R01. The effect size estimates we produce in this study and the attrition that we observe will allow us to determine if the effect of the PC personnel training is in the same range as effects seen in other studies. These estimates will inform the sample size we

SOCIAL PROTOCOL (HRP-580)**PROTOCOL TITLE:****VERSION DATE:**

propose in a subsequent R01 application; without the estimates from the present study we may significantly over or under estimate the sample size needed.

Based on the estimates we generate from the current study, we will run Monte Carlo simulations in MPlus to determine reasonable sample sizes for our R01 application. We will conduct these simulations to determine optimal sample sizes and allocation ratios between study arms. In addition, using the estimates of effect sizes, variance components, and attrition, we will model various analytic strategies and measurement approaches. We will conduct these advanced simulations with support and consultation of the college's Research Methodology Consulting Center.

17.2 Power Analysis:

NA

17.3 Statistical Analysis:

See section 17.1

17.4 Data Integrity:

The PI, in collaboration with the data safety monitoring committee, will monitor the data integrity. In weekly meetings with the project manager, the PI will review the data collected that week, that random assignment with blinding is carried out appropriately, and that data is being collected securely and in accordance with best practices. A brief report of the data integrity will be included in twice annual updates to the data safety monitoring committee.

18.0 Health Information and Privacy Compliance**18.1 Select which of the following is applicable to your research:**

My research does not require access to individual health information and therefore assert HIPAA does not apply.

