26.0 Resources Available

26.1 Resources Available:

Between the two primary collaborating clinics, there are approximately 50 providers, as well as residents and fellows who see children in this age range. Half of the participants will be randomly assigned to each study arm; n=15 of the 35 will be recruited for focus groups. If we fall short of this sample size (either because of sampling difficulty or if nurses are selected as the personnel to be trained), we will expand recruitment to other Hennepin Healthcare clinics, of which there are 6. Participants will receive \$50 for participating in each survey and \$100 for focus group participation.

[name] (PI) has 24% of his time in 2021 and 30% of his time in 2022-2024 dedicated to this project, including this stage and a later stage submitted under a separate IRB. [name], Project Manager, has 30% of her time dedicated to this project. Other partners have also dedicated time to support, including [name] (Co-I).

SOCIAL PROTOCOL (HRP-580)

PROTOCOL TITLE:

VERSION DATE:

Drs. [name] has access to adequate office space and office resources in Family Social Science. Resources include: individual offices and workstations with private phones and voicemail, fax capabilities, secure Internet access, and locking file cabinets for research teams; training and conference rooms available free of charge for sponsored projects. The project has staff support through the Center for Applied Research and Educational Improvement business office with expertise managing federal grant funds, HR, and Finance.

To safeguard against frustration and stress of PC personnel, all personnel will be encouraged to share concerns or issues with Drs. [name] and/or [name]. It will be stressed that all concerns provide useful information and opportunities to improve the protocol. In the unlikely event that PC personnel experience psychological strain, they will be provided a list of mental health professionals.

The PI and Project Manager will meet weekly to review study progress and assess any needs relating to the study protocol and procedures. The data safety committee will review study progress and assess needs twice annually.

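### Trained and control providers are randomised within the same two clinics for a year, and the plan lists nothing to limit or gauge sharing of the training, so the year-end effect sizes passed to the R01 could be diluted by an unknown amount

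*Combined protocol and SAP*

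**What the plan says.** Section 5.1 sets the unit and place of randomisation: "We will randomize PC personnel within two FQHC clinics to receive training or to a control group in which they only receive the information". Section 11.1 gives the sample, "We plan to enroll 35 medical providers who work with children between three-five years old at the two clinics", and the allocation, "Half of the participants will be randomly assigned to each study arm". Section 26.1 describes the pool: "Between the two primary collaborating clinics, there are approximately 50 providers, as well as residents and fellows who see children in this age range". The same section allows recruitment to extend to six other clinics if numbers fall short.

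The training (Section 4.1) covers how to present the benefits of parenting programs, how to answer common barriers, and how to motivate and refer parents. It consists of a 30-minute online introduction and an in-person session of about an hour. Controls receive the written referral process and no training (Section 1.1). Section 4.1 says the aim is to isolate the training over and above that process.

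The primary outcome is referral rates (Section 3.1), counted per provider over the pilot year (Section 5.2). Communication skills, the secondary outcome, are scored from vignettes listed for the post-training and post-pilot surveys. The one survey block listed for the post-pilot survey alone concerns declined referrals: "Whether clinician made any referrals, parent responses, whether and how frequently parents declined a referral, and reasons for declining (5 items". The focus-group topics are acceptability, appropriateness and feasibility. The only instruction not to share (Sections 14.1 and 20.2) concerns focus-group discussions, which come after the pilot year.

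Section 17.1 compares training with control, adds covariates, and looks at clinic differences and intra-class correlations. On the use of the results it says: "The effect size estimates we produce in this study and the attrition that we observe will allow us to determine" whether the training effect lies in the range seen elsewhere. The estimates then feed the R01 sample size and Monte Carlo simulations.

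**The concern.** Ways of talking to parents, answers to common barriers and an online module can all pass between colleagues by conversation or a forwarded link. If that happens during the pilot year, control providers' referrals and post-pilot skills rise, and both year-end contrasts shrink. The contrast would then no longer be training against no training, which is what Section 4.1 sets out to isolate.

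This pilot does not claim a conclusive effectiveness result. Its main quantitative product is a set of effect sizes and variance components for the next trial. A small year-end difference could mean that the training is weak or that some of it leaked. The two explanations point to different R01 designs (randomise providers or clinics) and different sample sizes. The listed data contain no direct measure that would help tell them apart, and exposure cannot be recorded as it happens once the year is over.

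**Working it through.** **Inputs from the documents.** N = 35, half per arm, so 17 and 18 (Section 11.1). Benchmark effects of d = .50 to .66 "on some PC practice outcomes" and attrition of 0 to 15% (Section 17.1). Target power .80.

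**Inputs assumed.** Alpha .05, which is not stated but reproduces the plan's power figures. Dilution fraction c, for which the documents give no value.

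**1. The plan's own figures.** Two-sample t-test, noncentral t, 17 and 18 per arm, alpha .05:
- d = .66, two-sided: power .474. The plan states "power of .47 to detect an effect of .66".
- d = .66, one-sided: power .605. The plan states .61.
- d = .66, 80% power: 38 per arm, total 76. The plan's lower figure is 76.
- d = .50, 80% power: 64 per arm, total 128. With 15% attrition, 128 × 1.15 = 147.2, rounded up to 148 (128 / 0.85 gives 151). The plan's upper figure is 148.

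The plan's figures reproduce, so the same method can be used below.

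**2. Dilution model.** If controls acquire a fraction c of the training effect, then

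observed d = (1 − c) × true d,

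and the required N grows roughly as 1 / (1 − c)². With true d = .66 (two-sided .05; N is for 80% power, before attrition):

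| Assumed c | Observed d | Power at N = 35 | Total N |
|---|---|---|---|
| 0 | .66 | .47 | 76 |
| 10% | .66 × .90 = .594 | .40 | 92 |
| 20% | .66 × .80 = .528 | .33 | 116 |
| 25% | .66 × .75 = .495 | .30 | 132 |

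At c = 25% the observed effect falls from the top of the benchmark range (.66) to just below its bottom (.50).

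**3. Could dilution be recognised from the estimate itself?** The approximate standard error of an observed d = .66 is √(1/17 + 1/18 + .66²/(2 × 35)) = .347. The 95% interval is .66 ± 1.96 × .347, or −0.02 to 1.34. A shift of .07 to .17 in d cannot be seen inside that interval. Only separate information on exposure would suggest it.

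**4. How concentrated the sample is.** If all 35 came from the roughly 50 providers, 35/50 = 70% of them would be in the study. Residents, fellows or added clinics would lower that share, so it is an upper figure.

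**5. Which outcomes are exposed.** Referral rates accumulate over the whole year, and post-pilot skills follow it. Skills scored immediately after training come before the year of mixing and are little affected.

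**The case against.** The strongest reply is that the plan already holds partial signals. Section 5.1 and the data-collection paragraph of Section 5.2 survey both arms after training or review of the written process, and again after the pilot year. A clear early skills gap that later closes because control scores rise would suggest leakage. Little early gap would suggest weak training. Section 5.2 also plans a focus group or interviews with controls. This stands, and a reader should not infer that spill-over is wholly unobservable. But no analysis of control-arm change is planned, contamination is not among the listed focus-group topics, and one sentence in Section 5.2 gives the post-training survey to the training group only.

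A reader might also infer that the arms share patients or the same referral therapists, or that the survey certainly has no exposure question. The documents state neither kind of sharing. The survey and focus-group script are attachments that were not available, so the supportable statement is that no such item is listed.

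Three further points count against overstating the matter. The dilution fractions are assumed, and the shifts they produce are small beside sampling error at N = 35. Dilution pulls the estimate towards no effect and would not create a false benefit. And if the R01 also randomised within clinics, a diluted effect could be relevant to its sample size. These limit the weight of the point. They do not remove it: the R01 design is not stated, and without information on exposure the team cannot tell which effect it has estimated.

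**Conclusion.** The point holds as a possible bias that the visible plan does not address. Individual randomisation within clinics is confirmed, as are the year-long exposure of the primary outcome and the use of the estimates for the R01. No request to withhold content, exposure item or spill-over analysis is listed.

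It is tempting to conclude that the effect will be diluted, or that randomising individuals was a mistake. The documents support neither. They give no sharing rate, and individual randomisation is defensible for a pilot with two clinics.

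The size is illustrative only. With true d = .66, dilution of 10% to 25% would move the N for 80% power from 76 to between 92 and 132. This rests on the proportional model above, a two-sided alpha of .05, and the assumed fractions. It applies to referral rates and post-pilot skills, and hardly at all to skills measured straight after training. This is a cheap improvement that should be made before the pilot year begins.

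**What to change.** 1. **Limit sharing.** At the training session, ask trainees not to pass materials or techniques to colleagues until the post-pilot survey closes. Send the online introduction by individual link. Controls are already meant to receive no training; this only specifies the delivery.
2. **Ask about exposure.** Add two or three items for controls to the post-pilot survey, and a prompt to the control focus group, on whether they saw training materials or discussed the techniques with a trained colleague. Report the proportion descriptively. Do not estimate effects by exposure: splitting 17 or 18 controls is not a randomised comparison and is too imprecise.
3. **Use the vignettes already planned.** Give the post-training vignettes to both arms, and reconcile the sentence in Section 5.2 that names only the training group. Report control-arm change from post-training to post-pilot as an indirect signal.
4. **Carry the uncertainty forward.** In the planned Monte Carlo simulations, vary an assumed dilution fraction over a stated range. Use the exposure reports only to judge which values are plausible. The share of controls reporting exposure is not the fraction of the effect they acquired and should not be entered as such.

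The cost is a spoken request, individual links, a few survey items, one focus-group prompt, one descriptive comparison and one simulation parameter. There are two limits: self-reported exposure is imperfect, and control-arm change may also reflect experience over the year.

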9.0 Study Population

9.1 Inclusion Criteria:

Inclusion criteria for providers include being an advanced practice provider (Physician, Resident, or RN) currently seeing clients at Hennepin Healthcare clinics, being willing to participate in the research, and be willing to participate in a referral training.

Vulnerable populations will not be targeted for inclusion, although they will be included if they are advanced practice providers who meet the other inclusion criteria.

9.2 Exclusion Criteria:

There are no known criteria that would exclude participants from the final sample.

9.3 Screening:

Providers interested in participating will contact the research team. The research team will review the study procedures and eligibility criteria.

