12.0 Recruitment Methods

12.1 Recruitment Process:

Two partners at HCMC, Drs. [name] and [name], will share information by email to recruit providers.

12.2 Source of Participants:

Providers will be drawn from Hennepin Healthcare clinics.

12.3 Identification of Potential Participants:

Provider participants will then self-identify in response to email contacts by Drs. [name] and [name] at HCMC.

12.4 Recruitment Materials:

Providers will be recruited by sharing a flyer by email from Drs. [name] and [name]. A copy of the “Provider recruiting and expectations” flyer is attached.

12.5 Payment:

Provider incentives for surveys and focus groups. Providers will receive a \$50 gift card for survey completion at each time point (after the training and after the pilot year). A subset of providers will receive a \$100 gift card for focus group participation. The maximum amount of incentives would be \$200. Gift cards will be sent electronically using tango.com within a week following survey completion or focus group participation.

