17.0 Statistical Considerations

17.1 Data Analysis Plan:

In order to measure communication skills, we will code the audiorecorded responses to vignettes. Because the communication skills in the PC training will mirror the therapist skills in GenPMTO, we will adapt relevant components of the Fidelity of Implementation Rating System⁴¹ and two coders will rate the quality of response, accounting for confronting, teaching, supporting, and facilitating.

We will examine the preliminary effectiveness of the PC personnel training. We hypothesize that communication skills and referral rates, will both be higher in the training group compared to the control group. While this pilot study *is not meant to provide sufficient power for significance testing*, these hypotheses will guide our analyses. We will analyze differences between training and control groups on outcomes including communication skill and referral rates, using generalized linear multivariate regression. We will examine communication skill items individually and assess the psychometrics of the items as a scale and as indicators of a latent variable. Each outcome will be analyzed in a separate model. In the first analysis, we will only enter training condition as a dummy variable (i.e., t-test) to examine between group differences. In subsequent analyses we will include covariates to account for clinical experience and demographic variables. Primary covariates include discipline (i.e., family medicine or pediatrics department) and years of experience. We will also examine differences by clinic location and examine intra-class correlations. These analyses will be useful in guiding focus group topics, examining the usefulness of the survey items we adapt and create, and generating effect size estimates and variance components for a fully-powered trial. Finally, we will examine the indirect effect of the PC personnel training on parent engagement through the mechanism (mediation) of PC personnel communication skills. For mediation analyses, we will use path models in MPlus with bootstrapped indirect effects.

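### The two primary covariates are scheduled only in post-randomisation surveys, so the adjusted referral-rate models can lose providers whose referral counts are known

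*Combined protocol and SAP*

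**What the plan says.** Section 3.1: "The primary study outcome is referral rates". Section 5.2 takes this outcome from records: "In addition, we will request aggregate referral rate data from HCMC medical records", and "For each provider, we will request the number of children ages 2-5 seen during the pilot year and the number of referrals made". The count therefore does not depend on whether the provider answers a survey.

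Section 17.1 fits a separate model for each outcome. The first contains training condition alone and later ones add covariates: "Primary covariates include discipline (i.e., family medicine or pediatrics department) and years of experience".

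The Demographics row of the survey table in section 5.2 covers "Age, gender, race/ethnicity, discipline, years of experience, etc", timed after training and again at the end of the pilot year. The table in section 6.2 repeats this timing for the provider surveys. The earlier survey comes after assignment: "Providers will complete a survey immediately following their training or review of written referral process and after the pilot year". Section 12.5 pays for "survey completion at each time point (after the training and after the pilot year"), which again gives two time points and no baseline.

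No other individual-level source is described. At screening (9.3), "The research team will review the study procedures and eligibility criteria". Section 22.1 describes a consent link for review and signature. The records request covers children seen and referrals made. Focus-group demographics in 6.2 are held in aggregate. No section says what happens when a covariate is missing.

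**The concern.** Discipline and years of experience are fixed before the study starts, yet they are first asked after one arm has been trained and the other has read a written summary. A provider who answers neither survey has a known referral rate and no covariates, and ordinary regression software drops that row.

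Two things follow. The adjusted models use fewer providers than the records supply. The providers kept are also chosen by a behaviour that occurs after randomisation and follows different experiences in the two arms. A difference between the unadjusted and adjusted estimates would then mix the effect of adjustment with the effect of selection. The study's stated product is effect-size and variance estimates for planning a larger trial, so avoidable noise or selection in the adjusted estimates is worth removing.

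**Working it through.** **Inputs.** N = 35, half to each arm (11.1), taken as 17 control and 18 training because 35 is odd. Effect d = 0.66, with stated power .47 two-sided and .61 one-tailed (17.1). Attrition of 0–15% in other studies (17.1), borrowed here only as an assumed range for survey non-response. Alpha is not stated; 0.05 is assumed.

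**Step 1: reproduce the plan's power.** Two-sample t-test, noncentrality = d × √(n₁n₂/(n₁+n₂)) = 0.66 × √(17 × 18/35) = 1.95, with 33 degrees of freedom. Power is 0.474 two-sided and 0.605 one-sided, which agrees with the plan.

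**Step 2: both arms receive both surveys (5.1 and the later text of 5.2).** A provider is lost only by missing both. With 15% non-response at each, independently (assumption):
- Expected loss = 35 × 0.15² = 35 × 0.0225 = 0.79, about 1 provider.
- Standard error ratio at N = 34: √(35/34) = 1.015, a rise of 1.5%.
- Two-sided power with 17 and 17: 0.46.

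Positively correlated non-response would raise the loss towards Step 3.

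**Step 3: extreme case.** The same 15% miss both surveys:
- 35 × 0.15 = 5.25, so about 5 lost and 30 kept.
- Standard error ratio: √(35/30) = 1.08, a rise of 8%.
- Noncentrality = 0.66 × √(15 × 15/30) = 1.81; power 0.42 two-sided, 0.55 one-sided.

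**Step 4: controls receive only the end-of-pilot survey (opening text of 5.2).** That text gives the post-training survey to the training group and the end-of-pilot survey to both. Trained providers then have two chances to supply the covariates and controls have one. At 15% independent non-response per survey:
- Controls lost: 17 × 0.15 = 2.55.
- Trained lost: 18 × 0.0225 = 0.41.
- Standard error ratio: √[(1/14.45 + 1/17.60) / (1/17 + 1/18)] = √(0.1260/0.1144) = 1.05, a rise of 5%.
- With 14 controls and 18 trained, two-sided power is 0.43.

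The power figures ignore both the precision gained from the covariates and the degrees of freedom they use. The plan says it is not powered for testing, so they serve only as a yardstick for lost information.

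**The case against.** The case for leaving this alone has several parts.

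- **Dropping rows is an inference.** The plan does not specify complete-case analysis. That is right. It is the usual default where no rule is given, and the plan gives none.
- **Only the follow-on models are affected.** The condition-only comparison comes first and keeps every provider with a referral count. This stands, and it limits the importance of the point.
- **The loss may be trivial.** A provider must miss two surveys, each paid $50, the earlier one given directly after the training or handout. The 0–15% is attrition elsewhere, not the share answering neither survey here. A provider who withdraws may also lack a count, because 13.2 does not say whether counts are still requested. All this stands, so Step 3 is an extreme and not an expectation.
- **The gaps could be filled later.** Department could probably be obtained from the clinic partners, and a name-to-ID link is kept (18.9). Possibly so, but no such step is planned.
- **The source may be in material not seen.** The consent form, the attached survey and the flow diagram are not in the text reviewed. The point rests on the schedules in 5.2 and 6.2.

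A reader might also infer more than the documents support. One such reading is that the plan adjusts for a variable affected by treatment. It does not: training cannot change department or years of experience, so the issue is missingness alone. Another is that non-response in the training arm would materially bias the effect. No section indicates how non-responders' referral rates differ, and the only documented route to unequal missingness (Step 4) points to the control arm. A third is that the shift from unadjusted to adjusted estimate is itself an input to the larger trial. Section 17.1 names effect sizes, variance components and attrition, not that shift.

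**Conclusion.** The concern holds as a modest, easily corrected weakness in data collection. The primary covariates have no planned pre-randomisation source, and the adjusted referral-rate models can therefore rest on fewer and differently selected providers than the unadjusted one.

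The likely size is about 1 provider of 35 if both arms receive both surveys, and about 3 (2–3 of 17 controls, fewer than 1 of 18 trained) if controls receive only the later one. Five of 35 is an extreme, and the loss could be zero. These figures assume listwise deletion, 15% independent non-response per survey (except in the extreme case), and referral counts available for every non-responder.

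It would be wrong to conclude that the primary comparison is compromised. The unadjusted contrast keeps all randomised providers with a count, and the pilot makes no confirmatory claim.

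**What to change.** - **Sections 5.2, 6.2 and 22.1:** collect discipline and years of experience with the consent link, completed before randomisation, and record clinic then too. Amend the Demographics rows accordingly; these two items need not be asked again later.
- **Section 17.1:** fit the adjusted referral-rate models on all randomised providers with a referral count, using the enrolment values. Add one sentence on handling any covariate still missing.
- **Sections 5.1 and 5.2:** reconcile the statements on whether controls receive the earlier survey. Enrolment collection removes the effect on these covariates either way, but the conflict also bears on the other survey measures.

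The cost is slight. Two existing items move from the survey to a contact that already takes place with every provider, and clinic is added because the Demographics row does not name it. No visit is added.
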